5.0 Participant Selection

Approximately 400 adult hepatology patients with poor prognosis (identified by the ‘surprise question’ see below) will be randomized to receive either usual hepatic care (control group, N=200) or usual hepatic care with comprehensive palliative care services (intervention group, N=200). Any Vanderbilt patient admitted to the primary inpatient service of one of the study hepatologists with limited life expectancy may be eligible for participation. We expect a participation rate of ~75% (based on the participation rate of a similar study conducted by [name]), and no more than 10% of patients excluded based on eligibility criteria. We are powered to detect a 13% difference in readmission rate between treatment arms with 400 participants, assuming equal mortality across arms (see section 8.0, Statistical Analyses). As this is an internally funded study, we will have flexibility to enroll patients past the the accrual goal of 24-months in order to enroll 400 participants if necessary.

Inclusion Criteria:

- Inpatient at Vanderbilt University Medical Center with advanced liver disease, whose treating hepatologist indicates a ‘No’ response to the question, “Would you be surprised if this patient died within 1 year?”

Exclusion Criteria:

- Age < 18 years
- Inability to give written informed consent (patient or surrogate decision-maker)
- Inability to respond to questions in English
- Treating hepatologist denies permission to enroll
- Receiving hepatology care at non-Vanderbilt sites (to ensure appropriate follow-up)

Recruitment

Potential patients will be identified within StarPanel using hepatology service codes and/or attending physician name. Patients’ electronic medical records will be manually reviewed by study personnel to confirm preliminary eligibility. Once preliminary eligibility is established, the treating hepatologist will receive a prompt via email with a REDCap survey link to respond to the question, “Would you be surprised if this patient died within 1 year?” The ‘surprise question’ has been used in a variety of patient populations for prognosis and to evaluate appropriateness for palliative care^{25,26} and has shown specificity (69.3%) and

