8.0 Statistical Analyses

Power Calculations

Power calculation was conducted on the primary outcome (time to first hospital readmission) using Cox proportional hazards model accounting for competing risk of death.³⁹ Assuming 50% 1-year mortality in both arms of the expected study cohort (‘surprise question’ inclusion which is comparable to a 50% 1-year mortality rate), with type I error of 0.05 and power of 80%, the minimum detectable hazard ratio (HR) under sample size N=400 was calculated given varying hospital readmission rate in the usual care arm ranging from 0.5 to 0.9. The corresponding rate reduction in the intervention arm (DR) and the relative rate reduction (RDR) were also provided. See **Table 3**. To assess clinical rationale of the power calculation, 1-year hospital readmission rate was assessed from pilot data obtained from a retrospective data pull via the Research Derivative. Admission to a study hepatologist during a 3-month window was required for cohort inclusion, and subsequent admission data (1-year post ‘qualifying admission’) was analyzed. Of the 151 patients included in the pilot data, 93 patients (62%) were readmitted within 1 year of the qualifying admission with a 1-year mortality rate of 35%. This pilot cohort (35% mortality rate) may be healthier than expected study cohort. However, due to competing risk of death, we are not sure whether the 1-year readmission rate of 62% from the pilot cohort is an overestimate or underestimate of the target population. Nonetheless, the proposed sample size provides sufficient power (80%) to detect rate reduction

of 13% when the hospital readmission rate in the usual care arm is between 50% and 70%, which is comparable with the pilot data.

Table 3

Various risk of readmission in the usual care arm (R), and the corresponding minimum detectable hazard ratio (HR) and the corresponding inverse HR (1/HR), difference of risk of readmission (DR) and relative difference of the first readmission (RDR) under sample sizes N = 400 with power 80% and type I error 0.05.

N = 400				
R	HR	1/HR	DR	RDR
50%	0.67	1.5	13%	0.26
60%	0.69	1.4	13%	0.22
70%	0.71	1.4	13%	0.18
80%	0.73	1.4	11%	0.14
90%	0.74	1.4	8.3%	0.092

Analyses Plan

Demographic and clinical characteristics of the participants such as age, gender, etc. will be compared between the control and the intervention arms using Wilcoxon rank-sum test for continuous variables and Pearson's Chi-square for categorical variables.

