Aim 1: Time to first hospital readmission within 1-year post randomization will be compared across treatment assignment using Cox proportional hazards model, accounting for the competing risk of death and adjusting for relevant demographic and clinical characteristics. A less than 1 hazard ratio for the treatment group status implies reduced readmission rates in the intervention arm given equal mortality rates.

Aim 2: Days alive out of hospital within 6-months post randomization, total days in hospital and ICU within 1-year post randomization, number and cost of hospital admissions within 1-year post randomization, median length of stay per admission, number of transfers to hospice within 1-year post randomization, time to hospice placement after referral, survival, presence of advance directives within 1-year post randomization, presence of physical symptoms, transplant status listing (deferred, listed, declined), and number of completed liver transplants will be obtained via chart review and compared across treatment assignment using proportional odds model for ordinal outcomes, Cox proportional hazards model for time-to-event outcome and logistic regression for binary outcomes, adjusting for relevant demographic and clinical characteristics.

Aims 3 and 4: Both cross-sectional and longitudinal analysis will be conducted to compare between group differences in CLDQ. For the cross-sectional study, for each time point of data collection, linear regression with ordinary least square will be used with CLDQ as the dependent variable (DV) and treatment assignment (0 for control arm and 1 for the intervention arm) as the independent variable (IV) of interest adjusting for baseline CLDQ and potential confounding factors based on clinical and statistical considerations. A positive value of the regression parameter for treatment status indicates higher CLDQ in the intervention arm. For longitudinal analysis, linear mixed model will be adopted including follow-up time and the interaction between follow-up time and treatment group on top of the cross-sectional model. The interaction term is included to compare decreasing rate of CLDQ between groups with a positive value of the corresponding regression parameter indicating slower decline rate of CLDQ in the intervention arm.

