The same series of analyses for the CLDQ will be conducted for the PROMIS (depression, anxiety), ED-5D-5L, the Quality of End-of-Life Care patient and caregiver questionnaires, and the KCSS. Histogram of baseline secondary outcomes will be used to evaluate ceiling/flooring effect and degree of skewedness. Appropriate transformation such as log transformation will be considered for highly skewed secondary outcomes to improve efficiency. A positive value of the main effect for intervention status in the cross-sectional analyses and a positive value of the interaction effect in the longitudinal analyses indicate favorable intervention effect.

Aim 5: Summary descriptive measures such as mean, quartiles and standard deviation for continuous variables and frequencies for categorical variables will be provided for process outcomes from participants in the intervention arm to evaluate fidelity of the proposed intervention and generalizability of implementing a large-scale intervention program. The following data will be collected for each arm: percentage of patients with answered surprise question (stratified by provider), percentage of patients with a 'No' response to the surprise question (stratified by provider), percentage of patients with 'No' response to the surprise question who were approved for study enrollment (stratified by provider), percentage of intervention patients who received initial PC inpatient consult, percentage of patients who received scheduled follow-up telephone contact, percentage of patients who attended an appointment for care after referral was obtained, percentage of patients with completed questionnaires at each time point, percentage of patients who received Palliative Care materials, and percentage of patients who received an inpatient PC consultation upon hospital readmission during the intervention phase will be calculated.

Interim Analysis

Interim analysis will be conducted when N=30 and N=150 participants are enrolled and followed for at least 6 months to evaluate whether the study is feasible, study procedures are conducted as intended, and that there is not significant patient dropout for mortality or other reasons.

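### The quality-of-life analyses give no rule for deaths although half the patients are expected to die within a year, so a survival difference between arms could bias them

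*Combined protocol and SAP*

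**What the plan says.** In Section 8.0 (Statistical Analyses), Aims 3 and 4 have two analyses of the Chronic Liver Disease Questionnaire (CLDQ). The first is cross-sectional: "for each time point of data collection, linear regression with ordinary least square will be used with CLDQ as the dependent variable", adjusted for baseline CLDQ and other factors. Its coefficient is read directly: "A positive value of the regression parameter for treatment status indicates higher CLDQ in the intervention arm". The second is longitudinal: "For longitudinal analysis, linear mixed model will be adopted including follow-up time and the interaction between follow-up time and treatment group". The other scales follow the same route: "The same series of analyses for the CLDQ will be conducted for the PROMIS (depression, anxiety"), then the EQ-5D-5L, the satisfaction questionnaires and the caregiver stress scale. Section 7.2 schedules these at baseline, week 4 and months 3, 6, 9 and 12.

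The power calculation in the same section works from "Assuming 50% 1-year mortality in both arms of the expected study cohort". The pilot cohort had lower mortality: "93 patients (62%) were readmitted within 1 year of the qualifying admission with a 1-year mortality rate of 35"%.

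Neither document part says what happens to a patient's quality-of-life outcome after death. There is no rank or value for death, no joint model, no stated estimand and no sensitivity analysis. Survival and the one-item caregiver rating of the quality of dying are separate outcomes. Questionnaire completion is only described, under Aim 5.

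**The concern.** Patients who are alive and able to answer at month 12 are a subset formed after randomisation. If one arm keeps more frail patients alive, its responders include people who would have been absent from the other arm, and the two groups are no longer comparable.

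This is foreseeable on the plan's own terms. Section 1.0 cites a lung cancer trial of early palliative care with median survival of 11.6 v 8.9 months, and states that palliative care has lengthened survival. Section 7.2 describes the CLDQ as separating early from advanced cirrhosis and tracking clinical deterioration, so a link between score and risk of death is plausible. Aim 1 does account for death as a competing risk and conditions its reading of the hazard ratio on equal mortality. Aims 3 and 4 carry neither safeguard.

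At stake is a secondary conclusion: Aim 3 might attribute to quality of life a difference that comes partly from who survived to answer, or miss a benefit for the same reason.

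**Working it through.** **The plan's own figures.** Table 3 concerns the primary endpoint only; there is no power figure for quality of life. It reproduces. With events = 400 × R and power = Φ(√(400R)/2 × |ln HR| − 1.96), R = 50% and HR 0.67 give Φ(7.071 × 0.4005 − 1.96) = 0.81, and all five rows give 0.80 to 0.82.

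**Survivors per arm.** The arms are "control group, N=200) or usual hepatic care with comprehensive palliative care services (intervention group, N=200"). Assuming a constant hazard, survivors = 200 × (1 − m)^(t/12):

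| Month | m = 50% (plan) | m = 35% (pilot) |
|---|---|---|
| 1 | 189 | 193 |
| 3 | 168 | 180 |
| 6 | 141 | 161 |
| 9 | 119 | 145 |
| 12 | 100 | 130 |

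Non-response among the living reduces these further. At two-sided 0.05 and 80% power, the unadjusted detectable difference is (1.96 + 0.84) × √(2/n): 0.28 SD with 200 per arm and 0.40 SD with 100.

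**Unadjusted survivor bias at month 12, no true effect.** Assume a normal frailty variable L on which survival depends, with correlation ρ between L and CLDQ. If a proportion p die, the survivors' mean CLDQ is ρ × λ(p), where λ(p) = φ(z_p)/(1 − p). The values are λ(0.50) = 0.798, λ(0.40) = 0.644 and λ(0.35) = 0.570. The bias is ρ × [λ(intervention) − λ(control)]:
- 50% v 40%, ρ = 0.5: 0.5 × (0.644 − 0.798) = -0.077 SD
- 50% v 35%, ρ = 0.7: 0.7 × (0.570 − 0.798) = -0.160 SD
- 50% v 60%, λ(0.60) = 0.966: +0.08 SD at ρ = 0.5 and +0.12 SD at ρ = 0.7
- equal mortality with similar deaths, or ρ = 0: zero

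Under the constant hazard, the first two figures are about -0.05 and -0.10 SD at month 6.

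**With the planned baseline adjustment.** Assume baseline CLDQ has the same correlation ρ with frailty, and correlation r of 0.5 to 0.7 with follow-up CLDQ. Survival selection shrinks the variance of L by a fraction k = λ(λ − z), averaged over the two arms' survivors. The slope on baseline among survivors is β = (r − ρ²k)/(1 − ρ²k), and the adjusted bias is the unadjusted bias × (1 − β).

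| Mortality, ρ | k | r | β | Adjusted bias |
|---|---|---|---|---|
| 50% v 40%, 0.5 | 0.605 | 0.5 | 0.411 | -0.077 × 0.589 = -0.045 SD |
| 50% v 40%, 0.5 | 0.605 | 0.7 | 0.647 | -0.077 × 0.353 = -0.027 SD |
| 50% v 35%, 0.7 | 0.584 | 0.5 | 0.299 | -0.160 × 0.701 = -0.112 SD |
| 50% v 35%, 0.7 | 0.584 | 0.7 | 0.580 | -0.160 × 0.420 = -0.067 SD |

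Adjustment reduces the bias but does not remove it.

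**Simulation of both planned models.** Control mortality was 50%. Assumed CLDQ parameters were a mean of 4, a fall of 0.5 points over the year and residual SD 0.6, with death tied moderately or strongly to each patient's level and slope. Baseline-adjusted regression at month 12 with no true effect gave -0.06 to -0.08 points at 40% intervention mortality and -0.10 to -0.15 at 30%. A true +0.30 at 40% mortality was estimated as +0.22 to +0.25. When death was unrelated to CLDQ, the estimates were unbiased.

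The mixed-model time-by-treatment slope was -0.07 (40%) and -0.18 (30%) under strong dependence. These runs had few replicates. One equal-mortality run, where symmetry requires zero, returned -0.08. I take from them only that the mixed model cannot be assumed to remove the problem, not a size.

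**The case against.** The strongest reply has five parts.

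- **Survivors only.** A reader might infer that quality of life is compared only among survivors. It is not: the mixed model also uses the earlier scores of patients who later die. That stands, and it limits the survivor-only description to the per-visit regression. The mixed model still treats values after death as missing and fills them in by implication, under no stated assumption.
- **Direction.** A reader might also infer that a survival benefit would necessarily appear as worse quality of life. The documents do not support that. It needs the additional survivors to score lower than the others. Even then, in the simulation above, a true benefit was attenuated and not reversed.
- **Equal mortality.** The plan assumes the same mortality in both arms, under which the bias is zero if the deaths are also similar. But that is a power assumption, and survival is itself an outcome that the intervention might change.
- **Size.** After adjustment the bias is below one standard error at month 12, which is √(1/100 + 1/120) = 0.135 SD unadjusted, and it is smaller at earlier visits. This stands, and it is why the point concerns secondary conclusions and is not a fatal flaw.
- **Remedy.** Ranking death with quality of life changes the question. At month 12 about half the patients would be tied at death, so survival alone could drive the result. Reporting quality of life among the living beside survival is a legitimate choice in palliative care. The composite has no clear meaning for caregiver stress or caregiver satisfaction. Section 5.0 also has surrogate-consented patients randomised before their baseline measures, so some will have no baseline score. All of this stands, and it argues for a supportive analysis of the patient scales and not a replacement.

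**Conclusion.** The point holds in a limited form. Aims 3 and 4 leave deaths unaddressed in a population where half are expected to die within the year. If mortality differs between arms and death risk is related to quality of life, both planned comparisons can be biased. A survival benefit could then mask or attenuate a quality-of-life benefit, and higher intervention mortality could create an apparent one.

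The month-12 regression bias is about -0.08 to -0.16 SD unadjusted and about -0.03 to -0.11 SD with baseline adjustment. Against the 0.40 SD detectable with 100 per arm, the unadjusted figures are one fifth to two fifths (0.08/0.40 and 0.16/0.40). They rest on assumptions that are not in the documents: intervention mortality of 40% or 35% against 50%, ρ of 0.5 to 0.7, r of 0.5 to 0.7, and normality. The mixed-model bias has not been sized reliably. The primary endpoint is unaffected.

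**What to change.** In Section 8.0 (Statistical Analyses), Aims 3 and 4:

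1. For the patient quality-of-life and mood scales only (CLDQ, EQ-5D-5L, PROMIS depression and anxiety), add a pre-specified supportive analysis at months 6 and 12. Rank death worse than the worst possible score, in the direction that applies to each scale. The model can be the one already named for Aim 2, "proportional odds model for ordinal outcomes", adjusted for baseline where available.
2. State how missing baselines (surrogate-consented patients) and missing scores in living non-responders are handled. Neither should be treated as a death.
3. Label the per-visit regression and mixed-model results 'among patients alive', and report them beside the number of deaths by arm at each visit.
4. State that no Aim 3 benefit or harm will be claimed from the survivor analysis without showing both the composite and its components.

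The planned analyses stay. The cost is wording and one further model per patient scale at two visits, with no new patients, visits or instruments. The downside is that the composite mixes survival with quality of life, so a result can be read only with both components shown.

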6.0 Intervention

We will conduct a randomized, controlled study to evaluate the impact of systematic, comprehensive palliative care services vs. usual hepatic care. After providing written informed consent, patients will complete baseline measures including demographic (**Appendix C**), mood, and quality of life questionnaires on the inpatient unit. Patients will be randomized to either the control (usual hepatic care) or the intervention arm (usual hepatic care with comprehensive palliative care services). Patients who are randomly assigned to usual care will not be scheduled to meet with the palliative care service unless a meeting is requested by the patient, the family, or the treating physician.

Patients randomized to the intervention arm will receive a binder (**Appendix D**) of patient materials including general information about palliative care services, the COMPASS study, and templates to document information if the patient wishes (names of medicine, upcoming appointments, important contact information, etc.). Intervention patients will also receive , contact information printed on a magnet (**Appendix F**), a wallet card (**Appendix G**), and a one-page handout (**Appendix H**). A VUMC palliative care physician or nurse practitioner will meet with the patient and appropriate surrogate, caregiver, family members, etc. after randomization to provide a verbal overview detailing palliative care services and to provide the comprehensive initial consult. Appropriate palliative care providers will provide follow-up in-person consults while the patient remains inpatient per usual palliative care services.

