Questionnaire data will be captured electronically via online REDCap survey or via paper copy. All participants (patient and caregivers in both usual care and intervention arms) will complete outcome measures at the same frequency – at Baseline, 4 weeks, and at 3, 6, 9, and 12-months post randomization. Baseline measures will be completed using a provided computer tablet, or paper version if preferred, on the inpatient hospital unit. If participant discharges from hospital prior to completion of questionnaires, and at the subsequent time points, participants (caregivers and patients) will complete assessments over the telephone with the study coordinator administering the questionnaires and documenting participant response on the REDCap survey form, or participants will complete assessments at home by accessing the REDCap survey form online directly. If the patient or caregiver prefers to complete assessments online or is unable to be reached by telephone, the study coordinator will provide the participant with instructions to access the online survey via email reminder with the link to the survey. Study Coordinator will attempt to contact the participant for completion of assessments up to 7 days post scheduled time-point. If unsuccessful after 7 days or if the participant prefers, paper versions of the assessments for the participant (patient or caregiver) and a stamped addressed envelope to return the completed assessments will be mailed.

If the patient returns to hospital and is inpatient at a scheduled assessment time point, the SC will meet with the patient or caregiver in-person to complete the assessments on the hospital unit by using a provided computer tablet or paper versions. See **Table 2** for the schedule of outcome assessments. If the study

participant dies while active in the study, a one-time, one-item survey will be completed by the caregiver 3 months after the death of the participant to gauge quality of death and dying.

Table 2

Schedule of Assessments						
Instrument	Baseline	Month 1 (Wk 4)*	Month 3 (Wk 13)*	Month 6 (Wk 26)*	Month 9 (Wk 39)*	Month 12 (Wk 52)*
Study Participant						
Demographic survey	X					
CLDQ	X	X	X	X	X	X
EQ-5D-5L	X	X	X	X	X	X
PROMIS Depression 4a	X	X	X	X	X	X
PROMIS Anxiety 4a	X	X	X	X	X	X
Quality of End-of-Life Care: Patient Questionnaire**	X	X	X	X	X	X
Caregiver						
Demographic survey	X					
Quality of End-of-Life Care: Caregiver Questionnaire**	X	X	X	X	X	X
Kingston Caregiver Stress Scale (KCSS)	X	X	X	X	X	X

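### Aims 3 and 4: the longitudinal model is judged only by a difference in slopes, which is zero for an early, sustained benefit and can contradict the visit-by-visit results

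*Combined protocol and SAP*

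**What the plan says.** Section 8.0, Aims 3 and 4, describes two analyses of the CLDQ.

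- **Cross-sectional:** "for each time point of data collection, linear regression with ordinary least square will be used", with treatment as the variable of interest and "adjusting for baseline CLDQ and potential confounding factors". A positive treatment coefficient means a higher CLDQ in the intervention arm.
- **Longitudinal:** a linear mixed model that adds follow-up time and the "interaction between follow-up time and treatment group on top of the cross-sectional model". Its stated purpose is: "The interaction term is included to compare decreasing rate of CLDQ between groups". The reading is a "positive value of the corresponding regression parameter indicating slower decline rate of CLDQ in the intervention arm".

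The next paragraph extends both analyses to PROMIS depression and anxiety, the EQ-5D-5L, the patient and caregiver satisfaction questionnaires and the KCSS. It gives one sign rule for all of them: a positive treatment effect is favourable in the cross-sectional analyses, and "a positive value of the interaction effect in the longitudinal analyses indicate favorable intervention effect". For the mixed model, no average, visit-specific or joint test of treatment is named.

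Section 7.2 sets the assessments "at Baseline, 4 weeks, and at 3, 6, 9, and 12-months post randomization". In Section 6.0 the intervention starts with a palliative care clinician meeting the patient "after randomization to provide a verbal overview detailing palliative care services and to provide the comprehensive initial consult".

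**The concern.** The interaction measures whether the arms drift apart or together between the first and last follow-up visit. It does not measure whether they differ. The consult and materials come soon after randomisation, and the first follow-up score is at week 4, so a gain already present at the first follow-up is plausible. If that gain is held, the pooled analysis has nothing to detect. If it wanes, the pooled analysis points the other way.

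The mixed model is the only planned analysis that uses all visits together, in a cohort planned at 50% one-year mortality. The visit-level regressions could then favour the intervention while the mixed model shows a null or negative result, and the plan does not say which of the two is the finding. Aims 3 and 4 rest on these scales.

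**Working it through.** **1. No stated figure to reproduce.** The documents give no SD, correlation, effect size or power for any questionnaire. The power calculation and Table 3 concern the primary outcome only.

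**2. Algebra (needs no variance assumption).** Baseline is a covariate, so the outcome rows are the follow-up visits. With linear time t, the modelled treatment difference is d(t) = b1 + b2·t, where b2 is the interaction.
- Benefit c present at the first follow-up and held: d(t) = c, so b2 = 0 whatever the size of c.
- Benefit falling from 0.4 at month 1 to 0 at month 12: b2 = -0.4/11 = -0.0364 per month, although d(t) is never below 0.
- Benefit growing linearly from 0 at randomisation to 0.4 at month 12: b2 = 0.4/12 = 0.0333 per month.

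**3. Inputs for the illustration.**
- From the documents: 200 per arm; one-year mortality 50% (planning value) or 35% (pilot); follow-up visits at months 1, 3, 6, 9 and 12.
- Assumed: constant death hazard; 10% non-response at each visit; after baseline adjustment, random-intercept SD 0.7, random-slope SD 0.04 or 0.08 per month, error SD 0.7; two-sided 5% level.

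**4. Formula.** Standard errors (SE) come from the expected generalised-least-squares information. Power = Φ(|effect|/SE - 1.96). The mean visit time is 31/5 = 6.2 months, so the average benefit is 0.3 for the constant pattern, 0.4 × (1 - 5.2/11) = 0.211 for the fading pattern, and 0.0333 × 6.2 = 0.207 for the growing pattern.

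**5. Worked case (50% mortality, slope SD 0.04).** SE of slope 0.0121 per month; SE of average 0.0903.
- Constant: slope test 5% in either direction (2.5% favourable). Average: Φ(0.3/0.0903 - 1.96) = Φ(1.36) = 91%.
- Fading: slope significantly negative Φ(0.0364/0.0121 - 1.96) = Φ(1.05) = 85%. Average: Φ(0.211/0.0903 - 1.96) = Φ(0.38) = 65%.
- Growing: slope Φ(0.0333/0.0121 - 1.96) = Φ(0.79) = 79%. Average: Φ(0.207/0.0903 - 1.96) = Φ(0.33) = 63%.

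**6. Range.**

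| Mortality, slope SD | SE slope | SE average | Constant: slope / average | Fading: slope negative / average | Growing: slope / average |
|---|---|---|---|---|---|
| 35%, 0.04 | 0.0110 | 0.0867 | 5% / 93% | 91% / 68% | 86% / 66% |
| 35%, 0.08 | 0.0137 | 0.0987 | 5% / 86% | 76% / 57% | 68% / 55% |
| 50%, 0.04 | 0.0121 | 0.0903 | 5% / 91% | 85% / 65% | 79% / 63% |
| 50%, 0.08 | 0.0151 | 0.1033 | 5% / 83% | 68% / 53% | 60% / 52% |

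**7. The planned visit-level regressions, same worked case.**
- Week 4: 200 × 0.944 alive × 0.9 = 170 per arm; SD = √(0.49 + 0.0016 + 0.49) = 0.991; SE = 0.991 × √(2/170) = 0.107. Power is about 80% for the constant 0.3 and 96% for the fading pattern (0.4 at that visit).
- Month 3: about 74% for the constant pattern and 81% for the fading pattern.
- Month 12: 90 per arm; SD = √(0.98 + 0.0016 × 144) = 1.10; SE = 0.164. Power is 45% for the constant pattern. With slope SD 0.08, SD = √(0.98 + 0.0064 × 144) = 1.38, SE = 0.206 and power is 31%.

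These are per-visit figures with no multiplicity adjustment.

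**8. Sensitivity to the set-up.** A second set of assumptions used total SD 1, between-visit correlation 0.5 or 0.7, random-slope variance 0 or 0.2, one-year loss 0-50%, and benefits in SD units. A sustained 0.3 SD still gave the slope test 5%, against 99-100% for the average. A fade from 0.4 SD to 0 gave a significantly negative slope 90-100% of the time, against 83-98% for the average. If baseline were an outcome row instead of a covariate, a sustained 0.3 SD would give a positive slope with power 40-76%, and the fading pattern would still give a negative slope (significant 22-87%).

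**The case against.** The strongest reply is that the visit-level regressions are an equal stated criterion in the same section and would pick up both patterns. That stands. For a benefit that fades completely, the planned week-4 comparison (96%) is more sensitive than the average difference proposed here (65% in the worked case). A reader might infer that the plan cannot detect an early benefit; step 7 shows otherwise. What remains is that each regression uses only that visit's responders, and nothing says what follows when they disagree with the pooled model.

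Second, a difference in slopes is a legitimate target. Section 6.0 continues telephone contact at least monthly for a year, and the Background cites an observational study in which early palliative care countered symptom progression. If benefit builds steadily, the slope test is the better one (79% v 63%). So a reader should not infer that the slope is an error. The weakness is in letting it stand as the only longitudinal criterion when the shape of the effect is unknown.

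Third, linear time is inferred from the talk of a rate and a single regression parameter; the plan does not say how time is coded. If visits are categorical, there are several interaction terms and a rule about one sign is undefined, so the text needs changing either way. The mixed model also contains a treatment term, but if time runs from randomisation that term is the difference extrapolated to time zero, and the plan assigns it no role in judging longitudinal benefit.

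Fourth, a reader might infer that the plan labels a fading benefit unfavourable. It never does. For the CLDQ a negative interaction means faster decline, and calling that unfavourable is the reader's step. The direction also holds only where higher is better. If higher PROMIS depression and anxiety or KCSS scores mean worse (an assumption from what they measure), a fading benefit gives a positive interaction, which the common rule would call favourable.

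**Conclusion.** The point holds for the longitudinal analysis of Aims 3 and 4, on the plain reading that baseline is a covariate and time is linear. The zero expected interaction for a sustained benefit is algebra. The powers are illustrative and rest on variances that the documents do not give: a constant 0.3-point benefit, slope test 5% against 83-93% for the average difference; a fade from 0.4 to 0, slope significantly negative 68-91% against 53-68% for the average; steady growth to 0.4, slope 60-86% against 52-66%.

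It does not show that the plan as a whole would miss an early benefit, because the visit-level comparisons would often show one. The outcomes are secondary and the primary analysis is untouched. The wording should be corrected before the data are analysed, because the pooled model could miss or contradict a real benefit and there is no rule for resolving the conflict.

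**What to change.** In Section 8.0, Aims 3 and 4:

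- Delete the rule that a positive interaction indicates a favourable effect in the longitudinal analyses.
- Fit one mixed model per scale with visit as a category, treatment, treatment by visit, baseline score and treating hepatologist (the stratification factor in Section 5.0).
- Name the treatment difference averaged over the follow-up visits as the lead estimate for each scale. Report the visit-specific differences from the same model, and keep the slope difference as a secondary description.
- State the favourable direction separately for each scale.
- State that, with high expected mortality, the model-based average implicitly extends scores past death, and show the visit-specific comparisons among survivors beside it.

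The cost is analysis-plan wording only. Power is somewhat lower if benefit builds steadily (63% v 79% in the worked case), and the average is less sensitive than the week-4 comparison to a benefit that disappears completely. The number of estimates per scale does not fall, since visit differences and slope are still reported; the change is that one of them is named in advance as leading.
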